7.7. Toxicity Management

Nebulized RDV will be administered to participants under close supervision.

Inhaled Remdesivir for Injection formulation will be administered to participants at the clinical site (Parts A and B). Healthcare professionals administering inhaled Remdesivir for Injection formulation should have the appropriate medication available for immediate use in case of hypersensitivity. The participant should be treated according to the SOC for management of hypersensitivity reaction. After dose administration, monitoring should be done as follows:

- Approximately 30 minutes after dose administration, participants should be observed, and vital signs should be performed prior to discharge (Parts A and B only)

Remdesivir for Inhalation Solution formulation may be administered to participants in the participant's home with in-person or telehealth support (Part C only). Healthcare professionals overseeing Remdesivir for Inhalation Solution formulation therapy remotely will observe the patient for any signs of adverse event. If any adverse event is observed and cannot be managed remotely, appropriate urgent care measures will be implemented.

- Approximately 30 minutes after dose administration, participants should be observed remotely prior to telehealth support session concluding

For participants with pre-existing pulmonary conditions (ie, COPD or asthma) enrolled in Part C of the study, prescribed inhalers may not be used \leq 30 minutes prior to Remdesivir for Inhalation Solution formulation administration.

The participant should be treated according to the SOC for management of hypersensitivity or bronchospasm according to site or home health protocol. The medical monitor should be notified prior to study treatment discontinuation when medically feasible. Study treatment dosing in an individual participant will be placed on hold and may be permanently discontinued, following review of all available clinical data by the Medical Monitor and discussion with the investigator, in the following conditions:

- Development of ALT levels $\geq 5 \times$ ULN
- Development of ALT levels $\geq 3 \times$ ULN **and** bilirubin $\geq 2 \times$ ULN
- Acute anaphylactic reaction to RDV
- Estimated creatinine clearance < 30 mL/min based on the Cockcroft-Gault formula
- Any SAEs and Grade 3 and 4 abnormal laboratory results assessed as related to study treatment

For clinical queries, please contact the medical monitor. Study treatment dosing may be resumed if it was held due to laboratory abnormality and is now within acceptable range, if the abnormality was not attributed to study treatment.

Please refer to [Appendix 4](#) for further details on the management of clinical and laboratory AEs.

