1.4. Risk/Benefit Assessment for the Study

Potential risks of a participant's study involvement include unknown adverse events (AEs) due to inhaled RDV. Strategies to mitigate these risks include close monitoring of participant's clinical status and laboratory testing. Parameters for discontinuation of the study treatment due to AEs will be well defined and closely followed.

Transient, Grade ≤ 2, treatment-emergent elevations in alanine aminotransferase (ALT) and aspartate aminotransferase (AST) were observed with daily IV RDV administration in Phase 1 studies in healthy volunteers. Transaminases increased is a listed adverse drug reaction to RDV. However, due to the reduced systemic exposure to RDV compared to the IV regimen, it is anticipated that there will be a lower effect on ALT and AST. Nonetheless, liver function testing will be closely monitored during the study.

Remdesivir contains SBECID, an approved excipient. In nonclinical species, SBECID administration has been associated with kidney vacuolation and hypertrophy. However, nonclinical inhalation toxicology studies and available inhaled clinical data with SBECID support its use in the RDV clinical formulation.

Participants may or may not clinically benefit from participation in the study. If efficacious, benefits might include shorter duration or lower severity of COVID-19 symptoms or reduced progression to severe disease. They may also benefit from increased observations and evaluations by health care professionals. Data from this study may support further evaluation of inhaled RDV in patients with COVID-19.

During a pandemic, additional potential risks to participants may include adequate study treatment availability, interruptions to the study visit schedule, and adherence to protocol-specified safety monitoring or laboratory assessments. Refer to [Appendix 2](#) for further details on the risks and risk mitigation strategy.

Considering the above, the benefit-risk balance for this study is considered positive.

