3.6. Discontinuation Criteria

Study treatment dosing in an individual subject will be placed on hold and may be discontinued following a review of all available clinical data by the medical monitor and discussion with the investigator, if any of the following occurs:

- Any SAE or \geq Grade 3 AE suspected to be related to RDV
- Any elevations in ALT $\geq 5 \times$ upper limit of normal (ULN); or ALT $\geq 3 \times$ ULN and total bilirubin $\geq 2 \times$ ULN, confirmed by immediate repeat testing
- FEV₁ decline of $> 15\%$ at 30 minutes postdose compared with same day predose FEV₁

Discontinuation of study medication is not a seriousness criterion.

Subjects, who discontinue the study medication, should be encouraged to remain in the study and attend study visits as described in Section 6 (Study Procedures).

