6.13.1. Criteria for Discontinuation of Study Treatment

Study treatment may be discontinued in the following instances:

- Intercurrent illness that would, in the judgment of the investigator, affect assessments of clinical status to a significant degree. Following resolution of intercurrent illness, the subject may resume study dosing if supported by both investigator and Gilead medical monitor

- Unacceptable toxicity, or toxicity that, in the judgment of the investigator, compromises the ability to continue study-specific procedures or is considered to not be in the subject's best interest
- Lack of efficacy
- Subject request to discontinue for any reason
- Subject noncompliance
- Pregnancy during the study; refer to [Appendix 5](#)
- Discontinuation of the study at the request of Gilead, a regulatory agency, or an institutional review board (IRB) or independent ethics committee (IEC)
- Any SAE or \geq Grade 3 AE suspected to be related to RDV
- FEV₁ decline of $> 15\%$ at 30 minutes postdose compared with same day predose FEV₁
- Meeting toxicity management criteria necessitating discontinuation, refer to Section [7.7](#).

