7.3. Vital Signs, SpO₂, and FEV₁

Descriptive statistics will be provided by treatment group for vital signs (heart rate, blood pressure, and respiration rate), SpO₂, and FEV₁ as follows:

- Baseline value
- Values at each postbaseline time point
- Change from baseline at each postbaseline time point

Two types of baseline will be defined for vital signs. An overall baseline value will be defined as the last available value collected on or prior to the date/time of first dose of study drug. Day 1 pre-dose baseline is defined the same as the overall baseline. A pre-dose baseline per day for each of dosing days 2-5 will use the “Predose” record on that day as baseline. Change from baseline to a postbaseline visit will be defined as the postbaseline value minus the respective baseline value.

In the case of multiple values in an analysis window, data will be selected for analysis as described in Section 3.8.3. No formal statistical testing is planned.

Additionally, for FEV₁, the number and percentage of participants with > 15% reduction in FEV₁ at 10 minutes postdose compared with the same day predose FEV₁ will be summarized by study day through day 5.

Temperature will not be summarized due to different methods of measuring temperature.

A by-participant listing of body weight, BMI, vital signs (heart rate, temperature, blood pressure, and respiration rate), SpO₂, and FEV₁ will be provided by study part, participant ID number and visit in chronological order.

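### Protocol 3.6 and 7.7 both require a dose hold but list different triggers, with a direct conflict on ALT; separately, SAP 7.3 does not count the 30-minute FEV1 falls that trigger a hold

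*Protocol*

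**What the plan says.** Three protocol sections govern when dosing stops.

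- **3.6 Discontinuation Criteria** opens with the action to take: "Study treatment dosing in an individual subject will be placed on hold and may be discontinued following a review of all available clinical data". The triggers are any SAE, or an event of at least "Grade 3 AE suspected to be related to RDV"; ALT thresholds, with the condition "confirmed by immediate repeat testing"; and an FEV1 decline above 15% "at 30 minutes postdose compared with same day predose FEV₁".
- **6.13.1 Criteria for Discontinuation of Study Treatment**: "Study treatment may be discontinued in the following instances". It repeats the related SAE/Grade 3 item and the 30-minute FEV1 item. It then points to 7.7 as if the criteria there made discontinuation necessary.
- **7.7 Toxicity Management**: dosing must be held, and may be permanently stopped after medical monitor review. Its triggers are the same ALT and ALT-with-bilirubin thresholds with no repeat test, acute anaphylaxis, creatinine clearance below 30 mL/min, and "Any SAEs and Grade 3 and 4 abnormal laboratory results assessed as related to study treatment".

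On these rules Protocol 1.4 states: "Parameters for discontinuation of the study treatment due to AEs will be well defined and closely followed".

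For FEV1, Protocol 6.10 schedules a test before dosing and at 10 minutes after dosing on every treatment day. A repeat at 30 minutes is scheduled only if the 10-minute value has fallen by more than 15%. SAP 7.3 counts participants with a fall above 15% "at 10 minutes postdose compared with the same day predose" value, by study day through Day 5. It also plans descriptive FEV1 statistics at each time point and a by-participant listing.

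**The concern.** Sections 3.6 and 7.7 impose the same obligation, a hold, on different sets of events. A site that keeps one of them to hand can continue dosing someone whom the other says to hold. Section 7.7 also carries the instructions for home and telehealth dosing in Part C, where the COPD and asthma exclusion no longer applies (Protocol 4.3), yet the FEV1 hold is missing from its list.

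The choice of rule also reaches the data. Under Protocol 7.6, a laboratory abnormality that leads to treatment interruption or discontinuation has to be recorded as an adverse event. Whether one unconfirmed ALT value leads to a hold can therefore decide whether an adverse event exists, and possibly whether it counts as one leading to discontinuation. The proportions with treatment-emergent adverse events and with such events leading to discontinuation are both secondary endpoints.

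The SAP issue is separate. The protocol has an explicit FEV1 safety criterion at 30 minutes, and no planned table reports how many participants meet it.

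**Working it through.** No figure in the plan bears on this point, so the check is a comparison of text, followed by the arm sizes.

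**1. The two hold lists side by side**

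| Trigger | 3.6 | 7.7 | Kind of difference |
|---|---|---|---|
| ALT at 5 times ULN or more; or ALT at 3 times with bilirubin at 2 times ULN or more | Listed, with repeat confirmation | Listed, no repeat | Conflict |
| Related SAE | Yes | Yes | None |
| Related non-serious clinical AE, Grade 3 or higher | Yes | Not listed | Omission from 7.7 |
| Related Grade 3 or 4 laboratory result | Only if recorded as an AE of that grade | Yes | Partial overlap; 7.6 lets AE and laboratory grades differ |
| FEV1 fall above 15% at 30 minutes | Yes | Not listed | Omission from 7.7 |
| Creatinine clearance below 30 mL/min | Not listed | Yes | Omission from 3.6 |
| Acute anaphylaxis | Not named | Yes | Omission by name; would usually be a related SAE |

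**2. Does applying both lists settle it?** For the omissions, yes: an event on either list leads to a hold. For ALT, no. If a single raised value is enough (7.7), the repeat-test clause in 3.6 has no effect. If the repeat is required (3.6), the unconditional item in 7.7 is too broad. Only one of the two can operate. The clause in 3.6 follows the second threshold after a semicolon, so it is also unclear whether it governs the first; the conflict exists for the second on any reading.

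**3. Section 6.13.1.** It has no hold step. It refers to 7.7 for criteria that require discontinuation, but 7.7 sets none: it requires a hold and permits discontinuation.

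**4. The FEV1 count.** The scheduled 30-minute test follows only a fall above 15% at 10 minutes. On any day, those meeting the 30-minute criterion are thus a subset of those in the SAP's 10-minute count, apart from extra tests done for suspected bronchospasm. With that exception, the SAP figure is an upper bound on participants meeting the hold criterion, not a count of them. Daily counts cannot simply be added to give participants affected on any day, because one person can appear on up to 5 days. For the same reason of selection, descriptive statistics at 30 minutes would come only from participants who had already fallen at 10 minutes or had raised clinical concern.

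**5. What one participant is worth.** Parts A and B: 36 / 3 = 12 per arm. Part C at 3:1: 80 × 3/4 = 60 and 80 × 1/4 = 20. One reclassified participant moves a proportion by 100/12 = 8.3 points, 100/20 = 5 points, or 100/60 = 1.7 points.

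**The case against.** Most of the differences are omissions. Neither list says that an unlisted event must not lead to a hold, so a careful site can apply both. That stands for every row except ALT, and it is why the point is not that the three sections contradict each other throughout.

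A reader might also infer more than the documents support.

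- *That the permissive wording of 6.13.1 conflicts with the mandatory hold.* It does not. It concerns discontinuation, which 3.6 and 7.7 also leave permissive.
- *That holds and discontinuations are not comparable across sites, or are biased between arms.* No between-site comparison of them is planned; the only by-site table is enrolment (SAP 4.1). Sites are blinded, so whichever list a site uses falls on all arms, and 3.6 and 7.7 both send the decision through the medical monitor.
- *That the SAP's 10-minute count adds to variation in holds.* An analysis table cannot change what sites do, and discontinuations are tabulated from the Study Drug Completion form and the AE data.
- *That the 10-minute count is wrong.* It is the post-dose test scheduled for everyone, so it has a full denominator. It is legitimate but incomplete.
- *That a creatinine clearance hold without a matching exclusion is a contradiction.* That is a design choice, and not part of this point.

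Finally, 7.7 refers to Appendix 4 for further management detail. Its body is not in the text available to this review, and it counts neither for nor against the plan.

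**Conclusion.** The point holds in a limited form. There is one direct conflict, on ALT confirmation. There are omissions on both sides, of which the 30-minute FEV1 fall and related non-serious clinical events of Grade 3 or higher matter most, because a site following 7.7 alone would not hold for them. The cross-reference from 6.13.1 to 7.7 also misdescribes what 7.7 says. On this text the stopping rules are not as well defined as Protocol 1.4 says.

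The number of participants affected cannot be derived. With arms of 12, 20 and 60, each one moves a proportion by 8.3, 5 or 1.7 points. The likely effect on the discontinuation endpoint is added noise. That rests on site blinding and on sites using one list for all their participants. Protocol 5.1.2 makes the study sponsor-unblinded and does not say whether the medical monitor who reviews holds is blinded, so the absence of bias is an inference and not a guarantee. The primary endpoint's definition does not depend on these rules.

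The SAP gap is real but independent: no table counts participants who meet the protocol's own FEV1 hold criterion.

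**What to change.** **Protocol.** Reconcile 3.6, 6.13.1 and 7.7 into one list in one section and replace the other two with cross-references. The sponsor needs to settle whether ALT needs repeat confirmation and for which threshold; which related events count; whether the FEV1, creatinine clearance and anaphylaxis items apply; and which triggers require a hold and which permit discontinuation. Appendix 4 should be checked against the result. This review does not say which rule is right.

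**SAP 7.3.** Keep the 10-minute count by day. Add, per arm, the number and percentage of dosed participants meeting the protocol's 30-minute criterion on any dosing day, with all dosed participants as the denominator. Show separately those with a 10-minute fall and no 30-minute repeat, so that a missed test is not read as recovery. Label any descriptive statistics at 30 minutes as coming from a selected subset.

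**Cost.** A protocol clarification and one table from FEV1 data already collected. The SAP is signed, and its Section 1 provides for later changes to be documented in the study report; the new table can be added on that basis.

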8. STATISTICAL CONSIDERATIONS

8.1. Analysis Objectives and Endpoints

8.1.1. Analysis Objectives

The primary objective of this study is:

- To characterize the impact of inhaled RDV on SARS-CoV-2 viral load in participants with early stage COVID-19

The secondary objectives of this study are:

- To evaluate the safety and tolerability of inhaled Remdesivir for Injection formulation in participants with early stage COVID-19
- To evaluate the PK of inhaled Remdesivir for Injection formulation and its metabolites in participants with early stage COVID-19 in Parts A and B
- To characterize and evaluate disease progression from baseline
- To characterize the efficacy, safety, and tolerability of Remdesivir for Inhalation Solution formulation administered with a mouthpiece in Part C of the study

CCI

8.1.2. Primary Endpoint

- Time-weighted average change in SARS-CoV-2 viral load which is defined as AUC of viral load change divided by time between baseline through Day 7

8.1.3. Secondary Endpoint

The secondary endpoints of this study are:

- Proportion of participants with TEAEs and laboratory abnormalities
- Proportion of participants with TEAEs leading to study treatment discontinuation
- Composite of all-cause MAVs (medical visits attended in person by the participant and a health care professional) or death by Day 28

- Composite of COVID-19 related MAVs (medical visits attended in person by the participant and a health care professional) or death by Day 28
- Proportion of participants hospitalized by Day 28
- Characterization of the plasma concentrations of inhaled RDV and its metabolites including AUC_{0-24h} , AUC_{last} , $CL_{ss/F}$, $t_{1/2}$, $V_{z/F}$, C_{max} , T_{max} , C_{last} , T_{last} , AUC_{tau} , λ_z , and C_{tau} (Parts A and B only)
- Change in SARS-CoV-2 viral load from baseline to Day 5
- Change in SARS-CoV-2 viral load from baseline to Day 7
- Change in SARS-CoV-2 viral load from baseline to Day 14 (Parts A and B only)
- Time to negative SARS-CoV-2 PCR
- Time to alleviation (mild or absent) of baseline COVID-19 symptoms as reported on the COVID-19 adapted FLU-PRO[©] questionnaire

CCI

A series of seven horizontal black bars of varying lengths, each preceded by a small black square. The first bar is relatively short, while the subsequent six bars are much longer, indicating significant redacted text.

8.2. Planned Analyses

8.2.1. Interim Analysis

Prior to the final analysis, interim analyses may be conducted and the analyses may be submitted to regulatory agencies to seek guidance for the overall clinical development program.

8.2.2. Final Analysis

The unblinded final analysis will be performed at the end of study, after all subjects have completed the study, outstanding data queries have been resolved or adjudicated as unresolvable, and the data have been cleaned and finalized.

8.3. Analysis Conventions

8.3.1. Analysis Sets

8.3.1.1. Efficacy

The primary analysis set for efficacy analysis is defined as the Full Analysis Set, which will include all participants who (1) are randomized into the study and (2) have received at least 1 dose of study treatment. Participants will be grouped according to the treatment to which they were randomized.

8.3.1.2. Safety

The primary analysis set for safety analyses is defined as Safety Analysis Set, which will include all participants who (1) are randomized into the study and (2) have received at least 1 dose of study treatment. Participants will be grouped according to the treatment which they received.

8.3.1.3. Pharmacokinetics

Each PK Analysis Set will include all randomized subjects who received at least 1 dose of study treatment and had at least 1 nonmissing PK concentration datum reported by the PK laboratory for each respective analyte.

8.3.2. Data Handling Conventions

Natural logarithm transformation for PK parameters will be applied for PK analysis.

For summary statistics, PK concentration values below the limit of quantitation will be treated as zero at predose and one-half of the lower limit of quantitation (LLOQ) for postdose time points.

Laboratory data that are continuous in nature but are less than the LLOQ or above the upper limit of quantitation, will be imputed to the value of the lower or upper limit plus or minus 1 significant digit, respectively (e.g., if the result of a continuous laboratory test is < 20, a value of 19 will be assigned).

Missing data can have an impact upon the interpretation of the trial data. In general, values for missing data will not be imputed. However, a missing pretreatment laboratory result would be treated as normal (i.e., no toxicity grade) for the laboratory abnormality summary.

All available data for participants that do not complete the study will be included in data listings.

8.4. Demographic and Baseline Characteristics Analysis

Demographic and baseline measurements will be summarized using standard descriptive methods.

Demographic summaries will include sex, race/ethnicity, and age.

8.5. Efficacy Analysis

8.5.1. Primary Analysis

SARS-CoV-2 viral load will be summarized by treatment using descriptive statistics in Part A and Part B. For Part C, time weighted average change in SARS-CoV-2 viral load will be compared between the RDV and placebo groups using analysis of covariance with baseline viral load included in the model as a covariate.

